# Insulet

Participant Duration	~15-17 weeks (allowing for screening and scheduling)
Study Duration (planned)	~8-10 months
Study Methods	
The study will consist of a 14-day standard therapy phase to capture baseline glycemic management followed by 13 weeks of treatment using the Omnipod 5 System. This is an outpatient study with unrestricted meals and activity, designed to emulate real world use. After the initial screening and enrollment visits, participants will have an in-clinic or virtual visit at least monthly. Devices will be returned at the end of the 13-week treatment period.
 
During the treatment period participants will undergo supervised exercise and meal challenges. Meal challenges will take place over 4 days. Meal challenges will consist of matched meals where participants will bolus on Days 1 and 3 for their selected meal. On Days 2 and 4 participants will consume a matched meal to Days 1 and 3 and not bolus. The exercise challenges will take place on 3 days and will consist of 1 hour of mild intensity and 30 minutes of moderate intensity exercise.

Statistical Methods	
A hierarchical testing scheme will be used to test for statistical significance of the change in the primary and key secondary outcomes listed above over 13 weeks of treatment.
 
The primary outcome of interest is HbA1c. Change in HbA1c will be tested for non-inferiority, comparing the HbA1c results from the Standard Therapy period to the Treatment period; if non-inferiority is established, superiority will be tested. The details are as follows:
 
 
Non-inferiority test for mean change in HbA1c from the Standard Therapy period to the Treatment period (e.g., HbA1cTreatment - HbA1cStandard = <math>\mu_{\delta}</math>) at alpha=0.025 with non-inferiority margin on 0.3%.
 
Superiority test (two-sided) for <math>\mu_{\delta} = 0</math> at alpha=0.05.
 
 
Summary statistics appropriate to the distribution will be generated for the Standard Therapy and Treatment periods, as well as for the difference (HbA1cTreatment – HbA1cStandard).
 
A paired t-test will be used to compare the change in HbA1c from Standard Therapy to the end of the Treatment periods. It is expected the change in HbA1c will follow a relatively normal distribution. If not normally distributed, robust regression using M-estimation with the Huber weight function will be used instead of a pair t-test. A point estimate and 95% confidence interval will be given for the mean change in HbA1c from baseline to 13 weeks.
 
If statically significant results (i.e., <math>p \geq 0.05</math>) are obtained for the primary endpoints, the key secondary outcomes will be tested hierarchical in the order listed above. If any of the key secondary outcomes fail to give a statistically significant result, then formal testing will stop and p-values will not be given for any outcomes further down on the list. Summary statistics and confidence intervals will be given for each outcome regardless of statistical significance. Note that each of the CGM metrics in the hierarchical listing refers to the overall 24-hour version.
 
All adverse events and additional safety outcomes listed above will be tabulated for each period (Standard Therapy and Treatment). The number of events and event rate per 100 person-years during the Treatment period will also be calculated.

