Endpoints	Safety Primary Endpoint: Change in HbA1c at 13 weeks from baseline 
 
• Tested first for non-inferiority (non-inferiority limit 0.3%) and then if non-inferiority is demonstrated, tested sequentially for superiority
 
 Additional Safety Endpoints: 
 
1. Severe hypoglycemia
 
2. Hospitalization/ER for severe hypoglycemia
 
3. Hyperosmolar hyperglycemic syndrome (HHS)/ diabetic ketoacidosis (DKA)
 
4. Hospitalizations or ER related to hyperglycemia or hypoglycemia in the previous 3 months vs. study 3 months
 
5. Other related serious adverse events
 
6. Reportable device-related adverse events
 
 Additional Key Secondary Endpoints The following secondary endpoints will be tested hierarchically if the primary HbA1c analyses for non-inferiority followed by testing for superiority are statistically significant 
 
1. Mean glucose (superiority)
 
2. Change in % time 70-180 mg/dL (superiority)
 

	
 
3. Change in % time 70-140 mg/dL (superiority)
 
4. Change in % time <math>\geq</math> 300 mg/dL (superiority)
 
5. Change in % time <math>></math> 250 mg/dL (superiority)
 
6. Change in % time <math>></math> 180 mg/dL (superiority)
 
7. % time <math><</math> 70 mg/dL (noninferiority; margin = 2.0%)
 
8. % time <math><</math> 54 mg/dL (noninferiority; margin = 0.5%)
 
9. T2-DDAS total score (superiority)
 
10. Change in % T2-DDAS total score <math>></math> 5.0 (high distress)
 
11. PSQI total score (superiority)
 
12. Change in % PSQI total score <math>\geq</math> 2.0 (poor sleep)
 
13. HCS total score (superiority)
 
14. Change in HCS total score <math><</math> 3.0 (low confidence)
 
15. % time <math><</math> 70 mg/dL (superiority)
 
16. % time <math><</math> 54 mg/dL (superiority)
 
17. Coefficient of variation (superiority)
 

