Population	
Inclusion Criteria:
 
Participants must meet all of the following criteria to be included in the study:
 
 
1. Age at time of consent 18-75 years
 
2. Diagnosed with type 2 diabetes, on current insulin regimen for at least 3 months prior to screening (i.e. Basal-bolus, basal only or pre-mix)
 
3. Basal bolus (long-acting insulin and rapid acting analog) or pre-mix users with A1C <math><</math> 12.0% OR basal users on long or intermediate acting insulin only with A1C <math>\geq</math> 7.0% and <math><</math> 12.0%
 
4. Willing to use only the following types of U-100 insulin during the study: Humalog U-100, Novolog, or Admelog
 
5. Participant agrees to provide their own insulin for the duration of the study
 
6. Stable doses over the preceding 4 weeks of other glucose-lowering medications as determined by Investigator
 
7. Stable doses of weight loss medications over the preceding 4 weeks and throughout the study that may affect glycemic control directly and/or indirectly, except for a dose reduction or discontinuation, as determined by Investigator
 
8. Willing to wear the system continuously throughout the study
 
9. Deemed appropriate for pump therapy per investigator's assessment considering previous history of severe hypoglycemic and hyperglycemic events, and other comorbidities
 
10. Investigator has confidence that the participant has the cognitive ability and can successfully operate all study devices and can adhere to the protocol
 
11. Able to read and understand English or Spanish
 
12. Willing and able to sign the Informed Consent Form (ICF)
 
13. If female of childbearing potential, willing and able to have pregnancy testing
 
 
Exclusion Criteria:

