Sample Size	Up to 400 screened participants to provide a cohort of 300 initiating use of the Omnipod 5 system and at least 275 completing the trial. A minimum of 60 and maximum of 125 participants using basal only.
Treatment Groups	Single-arm intervention that consists of 13 weeks of treatment using the Omnipod 5 System

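### Does the primary HbA1c test need a stated analysis set and missing-data rule in the Protocol Summary?

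*Combined protocol and SAP*

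**What the plan says.** The primary endpoint, in the Endpoints row of the Protocol Summary, is "Change in HbA1c at 13 weeks from baseline". The Statistical Methods row gives the test: "A paired t-test will be used to compare the change in HbA1c from Standard Therapy to the end of the Treatment periods". It then gives the fallback: "If not normally distributed, robust regression using M-estimation with the Huber weight function will be used instead of a pair t-test". The mean change is compared with a 0.3% margin at alpha 0.025 and then with 0 at two-sided alpha 0.05, and it is reported with a 95% confidence interval.

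The Sample Size row plans "a cohort of 300 initiating use of the Omnipod 5 system and at least 275 completing the trial". On case mix it adds: "A minimum of 60 and maximum of 125 participants using basal only". Inclusion criterion 3 sets a lower HbA1c limit for basal-only users but none for basal-bolus or pre-mix users.

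The 17 key secondary endpoints depend on the primary result: "The following secondary endpoints will be tested hierarchically if the primary HbA1c analyses for non-inferiority followed by testing for superiority are statistically significant".

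The summary does not name the population analysed. It does not say how a missing 13-week HbA1c is treated, and it lists no missing-data sensitivity analysis.

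**The concern.** Run literally, a paired t-test or a Huber fit to the change needs both HbA1c values, so anyone without a 13-week value drops out. The estimate would then describe those who were measured, not all who started the system. With no control group, there is no comparison arm with similar losses to offset the effect.

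Loss might plausibly follow baseline HbA1c or insulin regimen, and the cohort is mixed on both by design. The same mean change decides non-inferiority and superiority, and both gate the whole secondary hierarchy. A biased mean could therefore affect the primary safety conclusion and every formal test after it.

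**Working it through.** **Inputs from the Protocol Summary.** 300 starters; at least 275 completers; limits 0.3% and 0; 60 to 125 basal-only users. The shortfall allowed by the target is 300 - 275 = 25, and 25/300 = 8.3%. The summary gives no SD of change, expected effect or power, so the sample size cannot be reproduced.

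**Assumptions.** SD of change 1.0, 1.2 or 1.5; baseline-change correlation -0.5 or -0.3; 25 or 10 values missing.

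**1. Precision.** The 95% half-width is t x SD/sqrt(n). Going from 300 to 275 pairs, it moves from 0.114 to 0.119 (SD 1.0), 0.136 to 0.142 (SD 1.2) and 0.170 to 0.178 (SD 1.5). Non-inferiority power at a true change of 0 with 275 pairs is 99.9%, 98.5% and 91.1%. Lost precision is not the issue.

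**2. Bias in general.** Size of bias = (number missing/300) x gap, where the gap is the mean change in those lost minus that in those retained. With 25 missing, a gap of 0.5 gives 25/300 x 0.5 = 0.042 and a gap of 1.0 gives 0.083. With 10 missing the figures are 0.017 and 0.033.

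**3. Loss that depends on baseline HbA1c.** Let the chance of loss double per SD of baseline. For a normal baseline this shifts the mean of those lost by about ln 2 = 0.693 SD, so bias is about (missing/300) x 0.693 x |correlation| x SD.

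| Missing | Correlation | SD | Bias (points) |
|---|---|---|---|
| 25 | -0.5 | 1.0 | 0.029 |
| 25 | -0.5 | 1.2 | 0.035 |
| 25 | -0.5 | 1.5 | 0.043 |
| 25 | -0.3 | 1.2 | 0.021 |
| 10 | -0.5 | 1.2 | 0.014 |

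With the true mean exactly at a limit, simulation with 25 missing and correlation -0.5 gives an error in the device's favour of 7.3-7.4% if low-baseline participants are lost and 0.6-0.7% if high-baseline participants are lost, against a nominal 2.5%. With 10 missing (SD 1.2) the figures are 3.9% and 1.5%. Multiple imputation from baseline HbA1c and regimen brings all of these back to 2.2-2.7%.

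**4. Loss that depends on regimen.** Suppose mean change differs by 0.5 between regimens. If all 25 lost are basal-only, their share falls from 60/300 to 35/275 (bias 0.0727 x 0.5 = 0.036) or from 125/300 to 100/275 (bias 0.0530 x 0.5 = 0.027). If basal-only users are merely lost at twice the rate of others, bias is 0.006 to 0.008.

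**5. Loss that baseline does not explain.** With 25 missing, a gap of 0.5 gives an error of 6.6-10.5% for complete pairs and 6.6-10.5% after imputation. A gap of 1.0 gives 15.0-28.4% and 15.1-28.8%. Imputation does not help here.

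**6. Gap needed to change a conclusion.** With f = missing/300, completer mean m and gap d, solve m + f d + 1.96 sqrt(SD^2/(300 - missing) + f(1 - f)d^2/300) = limit. For example, with m = 0, SD 1.2, 25 missing and d = 1.77: 0.1475 + 1.96 sqrt(0.005236 + 0.000798) = 0.1475 + 0.1523 = 0.300.

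| Completer mean | Limit | 25 missing, SD 1.0/1.2/1.5 | 10 missing, SD 1.0/1.2/1.5 |
|---|---|---|---|
| +0.10 | 0.3 | 0.94/0.68/0.27 | 2.28/1.73/0.80 |
| 0 | 0.3 | 2.00/1.77/1.41 | 4.57/4.15/3.42 |
| -0.2 | 0 | 0.94/0.68/0.27 | 2.28/1.73/0.80 |
| -0.5 | 0 | 3.95/3.78/3.50 | 8.68/8.41/7.92 |

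A second calculation, pooling all 300 with a t quantile, gives 2.04/1.83/1.48 for the second row with 25 missing.

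**The case for a change.** The best case for a change is that the gap is on the page, the trial has no control arm, and one number gates everything. A completer mean of +0.10 (for non-inferiority) or -0.2 (for superiority) could be overturned by a gap as small as 0.27 if the SD is 1.5 and 25 values are missing. At the boundary, baseline-related loss can nearly triple the error rate, and imputation corrects it. The rule is cheap to write and is best fixed before data are seen.

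The arithmetic stands, and so does the point that a result close to a limit would need missing HbA1c examined. Four things weaken it as a case for amendment:

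- It argues from the silence of a summary. Naming a test does not rule out running it on imputed data, so complete-pair analysis is an inference.
- Completion is not the same as having a 13-week HbA1c. People who stop may still be measured, and completers may lack a value. The target is also not a cap, so the number missing could be above or below 25.
- The summary shows a mixed cohort, not selective loss.
- The largest errors, 15-28%, come from loss that baseline does not explain, which imputation leaves untouched. Imputing people who stopped from baseline HbA1c and regimen alone also treats them much like those who continued. That sits badly with an all-starters population that counts HbA1c whether or not the device is worn.

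**Conclusion.** No change to the plan is called for. This is detail missing from a summary, of a kind that analysts ordinarily settle sensibly. No stated rule is shown to give a wrong answer. If loss follows baseline HbA1c, complete pairs and a baseline-adjusted analysis would differ by about 0.03 to 0.04 points with 25 missing and correlation -0.5, and by about 0.014 with 10 missing and SD 1.2. If loss is unrelated to HbA1c change, there is no bias. Away from the limits neither primary conclusion is at risk: with 25 missing, overturning it takes a gap of 1.4 to 2.0 points at a completer mean of 0 (non-inferiority), or 3.5 to 4.0 points at -0.5 (superiority).

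This rests on assumed SDs of 1.0 to 1.5, assumed correlations and at most 25 missing values; the summary supplies none of the first two. The conclusion would be less comfortable if the completion target were badly missed or the observed mean fell close to 0.3% or 0. The full statistical section was not available and may already state the analysis set and the missing-data method.

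### As supplied, the Statistical Methods text opens the key secondary tests on p ≥ 0.05, the reverse of the plan's own significance rule

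*Combined protocol and SAP*

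**What the plan says.** All the relevant text is in the Protocol Summary of the combined protocol and SAP.

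- **Order of the primary tests (Statistical Methods).** Change in HbA1c is tested for non-inferiority first; "if non-inferiority is established, superiority will be tested".
- **Alphas (Statistical Methods).** Non-inferiority is tested "at alpha=0.025 with non-inferiority margin on 0.3" (in % HbA1c). Superiority follows: "Superiority test (two-sided) for \mu_{\delta} = 0 at alpha=0.05".
- **Step to the key secondary outcomes (Statistical Methods).** "If statically significant results (i.e., p \geq 0.05 ) are obtained for the primary endpoints", the key secondary outcomes are then tested in their listed order.
- **Stop rule (Statistical Methods, next sentence).** "If any of the key secondary outcomes fail to give a statistically significant result, then formal testing will stop".
- **Entry condition in words (Endpoints, Additional Key Secondary Endpoints).** The secondary endpoints "will be tested hierarchically if the primary HbA1c analyses for non-inferiority followed by testing for superiority are statistically significant". Seventeen ordered outcomes follow.

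**The concern.** The bracket is meant to say what counts as significant, but as supplied it describes a non-significant result. It is the only place in this text that attaches a numerical p-value condition to the step from the primary tests to the secondary hierarchy.

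At stake is whether a pre-specified rule is correct as written. The condition decides whether 17 ordered outcomes receive formal tests and p-values. Followed to the letter, it would withhold those tests after a successful primary analysis, which is exactly when the Endpoints section says they should proceed.

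**Working it through.** The check is one of logic. It needs no standard deviation, sample size or simulation.

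**Inputs, all from the Protocol Summary**

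| Item | Value | Section |
|---|---|---|
| Non-inferiority alpha | 0.025 | Statistical Methods |
| Superiority alpha | 0.05, two-sided | Statistical Methods |
| Order | superiority only after non-inferiority | Statistical Methods |
| Condition as supplied | p ≥ 0.05 | Statistical Methods |
| Entry condition in words | both primary analyses significant | Endpoints |
| Ordered key secondary outcomes | 17 | Endpoints |

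**Step 1. Do the two alphas agree with each other?** The sidedness of the non-inferiority test is not stated; 0.025 matches a one-sided test. The critical value for one-sided 0.025 is z = 1.960, and for two-sided 0.05 it is also z = 1.960. The alphas are consistent, and no choice of sidedness makes p ≥ 0.05 a significant result.

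**Step 2. Can a significant primary test meet the supplied condition?**

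- Non-inferiority shown: p < 0.025. Since 0.025 < 0.05, p < 0.05, so p ≥ 0.05 is false.
- Superiority shown: p < 0.05, so p ≥ 0.05 is false.

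That is 0 of 2 primary tests. If significance is written as p ≤ alpha instead, the only overlap is the single value p = 0.05 for superiority, which has probability zero for a continuous test statistic.

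**Step 3. What would the literal rule do?** There are two ways to apply it.

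- *To both primary tests.* Superiority is reached only if the non-inferiority p-value is below 0.025. A non-inferiority p-value of 0.05 or more means that superiority is never tested. The two parts cannot both be met, so the secondary tests never open.
- *To superiority alone.* The supplied condition holds when the 95% confidence interval for the mean change includes 0. The Endpoints condition requires that interval to exclude 0. The two are complements, so success on superiority always blocks the secondary tests.

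On either application, a successful primary analysis leads to 0 of 17 key secondary outcomes being formally tested.

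**Step 4. Compare with the stated alpha.** With no true change, the superiority p-value is uniform on 0 to 1. Taken on its own, the superiority condition is then met with probability:

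- as supplied: P(p ≥ 0.05) = 1 − 0.05 = 0.95
- with the sign turned round: P(p < 0.05) = 0.05, which equals the stated alpha.

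**Step 5. Compare with the stop rule.** The next sentence ends formal testing at the first outcome that is not significant. This is an ordinary fixed-sequence rule if significant means a small p-value. If the bracket's definition carried over, testing would stop at the first outcome with p < 0.05 and continue through those without. Only the bracket points that way.

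**The case against.** **The sign may be an artefact of conversion.** The text reviewed was read from PDF by a program. A ≤ is a natural way to write a significance threshold, and one misread would produce what we see. A reader might infer that conversion can be ruled out because ≥ is rendered sensibly elsewhere, for example in "Change in % time \geq 300 mg/dL (superiority" and "A1C \geq 7.0% and < 12.0". The documents do not support that inference. Those cases show only that ≥ came through as ≥. No ≤ appears anywhere in the supplied text, so nothing shows how one would have been rendered. Other slips in the same sentence suggest loose drafting, but they do not settle the origin of one symbol. This objection stands: the contradiction is certain in the supplied text, but its presence in the source is only probable.

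**Nobody would apply the rule literally.** This also stands, and it limits the severity. The Endpoints section gives the entry condition in words, and Statistical Methods gives both alphas and the stop rule. The intended rule can be recovered without the bracket. The figures 0 of 17 and 0.95 therefore describe a literal reading that no reasonable analyst would adopt; they do not measure a likely risk to the trial. Clear intent still does not make the sentence correct, and a decision threshold should be right where it is written.

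**The correction should also state a direction.** A reader might infer from the two-sided superiority test that the sentence must specify a fall in HbA1c. That is a separate matter. Both sections already call the test one of superiority, and the reversed sign can be shown and corrected without it.

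**Conclusion.** The point holds as a minor correction to a written decision threshold. In the supplied text, the condition for opening the key secondary hierarchy is reversed relative to the word it defines, both primary alphas, the stop rule and the Endpoints section. Literally applied, it would block all 17 key secondary outcomes after a successful primary analysis.

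Confidence is high that the supplied text contradicts itself, and moderate that the error is in the source document. The conclusion rests on no assumed quantity, only on the stated alphas and the usual meaning of a significant result.

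A reader might infer that the hierarchical design is unsound or that its error control is lost. The documents do not support this. The alphas are mutually consistent, the order of testing is fixed, and the stop rule is conventional. Only the bracket is at odds with them. The text reviewed is the Protocol Summary, so no inference is drawn about how the rule is worded in any fuller statistical section.

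**What to change.** 1. Check the symbol against the source PDF. If the source has the correct sign, no change is needed.
2. If it is reversed there, replace the sentence before analysis with, for example:

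> If non-inferiority is shown at alpha = 0.025 and superiority is then shown at two-sided p < 0.05, the key secondary outcomes will be hierarchically tested in their listed order.

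This is better than only turning the sign round, because a bare p < 0.05 would still misstate the non-inferiority threshold of 0.025. It restates alphas that the section already contains.

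The cost is one symbol check and at most one sentence of wording. Patients, data, alphas and analyses do not change.

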## Insulet

	
McNemar's test will be used to compare the percentage of participants with hospitalization or ER visits related to hyper- or hypoglycemia during the 13-week Treatment period compared with the 13-week period prior to enrollment.
 
All variables will be examined for normality of their distributions and, if applicable, standard residual diagnostics will be performed. If values are highly skewed, then a nonparametric or robust regression M-estimation method will be used instead.

--	---

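### Does giving a person-time event rate for Treatment only, and leaving the glucose CV window unstated, distort the comparison of a 14-day with a 13-week period?

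*Combined protocol and SAP*

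**What the plan says.** All references are to the Protocol Summary in the combined protocol and SAP.

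- **Period lengths (Study Methods).** The study has a "14-day standard therapy phase to capture baseline glycemic management followed by 13 weeks of treatment using the Omnipod 5 System".
- **Safety tables (Statistical Methods).** "All adverse events and additional safety outcomes listed above will be tabulated for each period (Standard Therapy and Treatment"). The next sentence reads: "The number of events and event rate per 100 person-years during the Treatment period will also be calculated". No matching rate is named for Standard Therapy.
- **The tested safety comparison.** McNemar's test compares the percentage of participants with a hospitalization or ER visit for hyper- or hypoglycemia "during the 13-week Treatment period compared with the 13-week period prior to enrollment". Additional safety endpoint 4 says the same: "in the previous 3 months vs. study 3 months".
- **Key secondary outcomes.** The hierarchical scheme tests "change in the primary and key secondary outcomes listed above over 13 weeks of treatment". CV, tested for superiority, is number 17 of 17. The CGM metrics are the 24-hour versions. No CV formula and no CGM window for Treatment are given.
- **Reporting.** "Summary statistics and confidence intervals will be given for each outcome regardless of statistical significance".

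**The concern.** Safety is the primary objective and the trial has one arm, so for most events the Standard Therapy column is the only comparator within the study. A count over 13 weeks beside a count over 14 days will be larger even if nothing has changed. The percentage of participants with an event has the same defect. With a rate in one column only, a reader cannot put the two on one scale from the table alone. The authors matched the windows for hospitalization and ER visits, but severe hypoglycemia and HHS/DKA, as endpoints in their own right, have no such look-back in the Summary.

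CV raises a similar question. A longer window takes in more slow drift in glucose, so a CV pooled over 13 weeks tends to exceed one pooled over 14 days. Mean glucose and percent-time metrics are averages and are not biased by unequal windows. If CV were pooled this way, a real reduction would be understated, and the understated change would be reported even if the hierarchy stopped earlier.

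**Working it through.** The documents give no event rate, event count, or mean or SD for CV, so there is no planned figure to reproduce. Inputs from the documents are 14 days, 91 days (13 weeks), 300 starting, at least 275 completing and up to 400 screened. Everything else is marked as assumed.

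**1. Exposure.** Person-years (PY) = n × days / 365.25.

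- Standard Therapy: 300 × 14 / 365.25 = 11.5 PY
- Treatment: 300 × 91 / 365.25 = 74.7 PY
- Ratio: 91 / 14 = 6.5

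The ratio assumes the same people in both periods with no dropout. If 400 people contributed 14 days (an upper bound) and 25 left halfway through Treatment (assumed), it becomes (275 × 91 + 25 × 45.5) / (400 × 14) = 26,162.5 / 5,600 = 4.7.

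**2. Expected counts at an unchanged rate (rates assumed), n = 300.** Expected count = rate × PY / 100; chance of no Standard Therapy events = exp(−expected count).

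| Rate per 100 PY | Standard Therapy | Treatment | Chance of zero in Standard Therapy |
|---|---|---|---|
| 5 | 0.6 | 3.7 | 56% |
| 10 | 1.1 | 7.5 | 32% |
| 20 | 2.3 | 14.9 | 10% |

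**3. What a Standard Therapy rate would tell the reader.** Exact Poisson 95% limits are χ²(0.025; 2k)/2 and χ²(0.975; 2k+2)/2, divided by PY and multiplied by 100.

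- 0 events in 11.5 PY: 0 to 32.1 per 100 PY
- 1 event in 11.5 PY: 8.7 (0.2 to 48.5)
- 7 events in 74.7 PY: 9.4 (3.8 to 19.3)

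With zero or one event, the Standard Therapy interval covers the whole Treatment interval in this example, so the added rate would not separate the periods.

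**4. Does the text fix the CV window?** The phrase about 13 weeks covers the primary and all key secondary outcomes together. HbA1c is compared at the end of Treatment, and the questionnaire scores are not averages over a sensor record. The phrase therefore says over what span change is assessed; it does not set a CGM averaging window. A mean of daily CVs, or windows of equal length, would carry no window-length bias.

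**5. Size of the CV effect if it is pooled over each whole period.** Take daily means with lag-one correlation ρ. Expected variance within an n-day window = s_w² + s_d² × (1 − mean of the n × n matrix ρ^|i−j|). CV inflation is the difference in square roots between n = 91 and n = 14, divided by the mean. All inputs are assumed: mean 170 mg/dL, within-day SD s_w 40 to 55, SD of daily means s_d 12 to 20.

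- ρ from 0 to 0.6: 0.05 to 0.55 points
- ρ of 0.8 to 0.9, with s_d widened to 12 to 25: 0.27 to 1.92 points

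A second model (long-run CV 30%, slow component 0 to 20% of variance, time constant 3 to 30 days, all assumed) gives about 0.2 to 1.7 points. Both models assume stationary glucose. If the mean is raised by 10 to 20 mg/dL in the first two weeks only, the 13-week CV falls from 30.0 to about 29.8, so the direction is not certain.

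**6. Consequence for the CV test.** Paired t, n = 275, two-sided 0.05, noncentrality = (effect − bias) / (SD/√275), SD of change 4 to 6 points (assumed).

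| True reduction | Bias | Power |
|---|---|---|
| 1.0 | 0 | 79–99% |
| 1.0 | 0.1 | 70–96% |
| 1.0 | 0.3 | 49–82% |
| 1.0 | 0.5 | 28–54% |
| 1.5 | 0.5 | 79–98% |
| 2.0 | 0.5 | at least 98% |

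With no true change, the chance that the whole interval lies on the worsening side is 13–24% at bias 0.3 and 5–6% at bias 0.1, against 2.5% without bias.

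**The case for a change.** The best case for a change is that it costs almost nothing. Person-years and an exact interval in both columns need a line of wording and no new data. The very imprecision of the Standard Therapy rate argues for printing it, because a bare zero or one hides how little it means. For CV, the plan leaves open the choice that creates the bias, and a window matched to the 14-day baseline would settle it. The plan also does not say whether the meal- and exercise-challenge days, at most 4 + 3 = 7 of 91, count in the CGM metrics.

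Much of this stands as good reporting practice. The side-by-side counts are on different exposures, and a careful analyst will show person-time for both. Severe hypoglycemia that led to no hospital or ER visit has no matched comparison in the Summary; episodes of severe hypoglycemia or HHS/DKA that did lead to one fall within the matched McNemar test.

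What does not stand is the step from there to a fault in the plan. The text specifies no between-period test of these events, so no inference is distorted. The text available is a synopsis, where CGM computing rules are often left out, so its silence is not evidence that unequal windows will be pooled. Saying that the challenge days count would only write down the natural default.

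**Conclusion.** No change to the plan is needed. The safety point is true as wording: events are tabulated for 14 days and for 13 weeks, and a rate is named for Treatment only. At an unchanged rate the counts would differ 6.5-fold, or about 4.7-fold under the assumed screening and dropout pattern above. This affects presentation only. Both durations are stated, the tested comparison is window-matched, and a Standard Therapy rate from 11.5 person-years would alter no conclusion. An analyst can add it from the same data without any amendment.

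The CV point is not established. It depends on pooling over each whole period, which the text does not specify, and on assumed variance components. If pooling were used, stationary models give 0.05 to 0.55 points for correlation up to 0.6, and up to 1.92 at the extreme inputs. In those models the effect runs against the device, so it would not create a false success. It would matter for power mainly if the true reduction were near 1 point. It concerns the last endpoint in the hierarchy, after which nothing is tested, and the HbA1c primary endpoint is untouched. A missing CV definition is a detail that analysts routinely settle when they specify the CGM metrics.
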